**Alopecia**  
Recent Hair loss (within last 30 days as reported by patient)

0-absent 1-present		
-----------------------	--	--

**Total Activity Score**  
(For the activity score, please add up the scores of the left side, i.e. Erythema, Scale, Excoriation, Ulceration, Gottron's, Periungual, Alopecia)

**Total Damage Score**  
(For the damage score, add up the scores of the right side, i.e. Poikiloderma, Calcinosis)

Copyright © 2008 University of Pennsylvania  
All Rights Reserved

### 8.2.23 MDAAT

The MDAAT is a combined tool which will capture the investigator's assessment of disease activity of various organ systems using a 0 to 4 point scale as well as a VAS for each disease activity component.

Extramuscular Global Assessment and Global Disease Activity components are the 2 CSMs used for TIS and DOW calculations.

**Figure 9: MDAAT**

Constitutional Disease Activity	(Absent)	(Maximum)	Examples of maximal score					
	—	— cm	Severe fatigue or malaise resulting in being bed bound and an inability to perform self care					
1. Pyrexia – documented fever > 38° Celsius			0	1	2	3	4	NA
2. Weight loss – unintentional > 5%			0	1	2	3	4	NA
3. Fatigue/malaise/lethargy			0	1	2	3	4	NA
Cutaneous Disease Activity	(Absent)	(Maximum)	Examples of maximal score					
	—	— cm	- Ulceration to muscle, tendon or bone; - Extensive erythroderma					
4. Cutaneous ulceration			0	1	2	3	4	NA
5. Erythroderma			0	1	2	3	4	NA
6. Panniculitis			0	1	2	3	4	NA
7. Erythematous rashes:								
a. with secondary changes (e.g. accompanied by erosions, vesiculobullous change or necrosis)			0	1	2	3	4	NA
b. without secondary changes			0	1	2	3	4	NA
8. Heliotrope rash			0	1	2	3	4	NA
9. Gottron's papules/sign			0	1	2	3	4	NA
10. Periungual capillary changes			0	1	2	3	4	NA
11. Alopecia:								
a. Diffuse hair loss			0	1	2	3	4	NA
b. Focal, patchy with erythema			0	1	2	3	4	NA
12. Mechanics hands			0	1	2	3	4	NA
Skeletal Disease Activity	(Absent)	(Maximum)	Examples of maximal score					
	—	— cm	Severe arthritis with extreme loss of function (bedridden, inability for self care)					

## 13. Arthritis:

- a. Severe active polyarthritis
- b. Moderately active arthritis
- c. Mild arthritis

0	1	2	3	4	NA
0	1	2	3	4	NA
0	1	2	3	4	NA

## 14. Arthralgia

Gastrointestinal Disease Activity	(Absent)	(Maximum)	Examples of maximal score					
			Major abdominal crisis requiring surgery or intensive care					
		— — . — cm						

## 15. Dysphagia:

- a. Moderate/severe dysphagia
- b. Mild dysphagia

0	1	2	3	4	NA
0	1	2	3	4	NA

## 16. Abdominal pain related to the myositis disease process:

- a. Severe
- b. Moderate
- c. Mild

0	1	2	3	4	NA
0	1	2	3	4	NA

Pulmonary Disease Activity	(Absent)	(Maximum)	Examples of maximal score					
			Active interstitial lung disease or respiratory muscle weakness requiring ventilatory support					
		— — . — cm						

17. Respiratory muscle weakness **without** interstitial lung disease (ILD):

- a. Dyspnea at rest
- b. Dyspnea on exertion

0	1	2	3	4	NA
0	1	2	3	4	NA

18. **Active reversible ILD** (i.e. not just ventilatory abnormalities due to pulmonary fibrosis):  
*Read glossary for scoring pulmonary function tests and score each item below (a,b and c).*

- a. Dyspnea or cough due to ILD
- b. Parenchymal abnormalities on chest x-ray or high resolution CT scan (HRCT) and/or ground glass shadowing on HRCT
- c. Pulmonary Function Tests:  $\geq 10\%$  change in FVC OR  $\geq 15\%$  change in DLCO

0	1	2	3	4	NA
0	1	2	3	4	NA

## 19. Dysphonia:

- a. Moderate to severe
- b. Mild

0	1	2	3	4	NA
0	1	2	3	4	NA

Cardiovascular Disease Activity	(Absent)	(Maximum)	Examples of maximal score					
			Myocarditis, pericarditis or severe arrhythmia requiring intensive care unit					
		— — . — cm						

## 20. Pericarditis

0	1	2	3	4	NA
0	1	2	3	4	NA

## 21. Myocarditis

0	1	2	3	4	NA
0	1	2	3	4	NA

## 22. Arrhythmia:

- a. Severe arrhythmia
- b. Other arrhythmia, except sinus tachycardia

0	1	2	3	4	NA
0	1	2	3	4	NA

## 23. Sinus tachycardia

Other Disease Activity	(Absent)	(Maximum)	Examples of maximal score					
			Extreme disease activity with major impact on function					
		— — . — cm						

## 24. Specify:

0	1	2	3	4	NA
0	1	2	3	4	NA

Extramuscular Global Assessment	(Absent)	(Maximum)	Overall evaluation for disease activity in all extramuscular systems (EXCLUDING MUSCLE DISEASE ACTIVITY)					
			Overall evaluation for disease activity in all extramuscular systems (EXCLUDING MUSCLE DISEASE ACTIVITY)					
		— — . — cm						

Muscle Disease Activity	(Absent)	(Maximum)	Examples of maximal score					
			Severe muscle weakness resulting in being bed bound and an inability to perform self care					
		— — . — cm						

## 25. Myositis:

- a. Severe muscle inflammation
- b. Moderate muscle inflammation
- c. Mild muscle inflammation

0	1	2	3	4	NA
0	1	2	3	4	NA

- a. Severe muscle inflammation
- b. Moderate muscle inflammation
- c. Mild muscle inflammation

0	1	2	3	4	NA
0	1	2	3	4	NA

## 26. Myalgia

Global Disease Activity	(Absent)	(Maximum)	Overall evaluation for the totality of disease activity in ALL systems, (INCLUDING MUSCLE DISEASE ACTIVITY)					
			Overall evaluation for the totality of disease activity in ALL systems, (INCLUDING MUSCLE DISEASE ACTIVITY)					
		— — . — cm						

Extramuscular global and global disease activity will be 2 of 6 CSMs used for TIS and DOW calculations

## 8.2.24 Study Drug Exposure

There are several levels of aggregation for study drug exposure.

Level 1: Observation in database extract.

Level 2: Infusion. One infusion may consist of more than one eCRF record. If there is more than one eCRF record completed with the same kit number, this is considered an infusion with an interruption. All eCRF records with the same value of Kit Number (as entered in the eCRF) belong to the same infusion.

Level 3: Day with infusions. More than one infusion may be performed on one day. All infusions with the same date of infusion (as entered in the eCRF) belong to the same day of infusion.

Level 4: Week. There can be more than one day with infusions in one week. All infusion days with the same value of Week (as entered in the eCRF) belong to the same week.

Level 5: Period. Weeks 1 to 24 belong to Study Period 1 (Week 1-25), weeks 25 to 52 belong to Study Period 2 (Week 25-53), weeks 53 to End of Study Period 3 belong to Study Period 3 (Week 53-EOP3).

**Table 6: Derivation of Exposure Variables**

Variable	Observation in database extract	Infusion	Day with Infusion	Week	Period
Planned Total Dose Volume per Week (mL)	n/a	n/a	n/a	entered	n/a
Actual Total Dose (g)	n/a	n/a	n/a	derived	sum
Actual Dose (g/kg bw)	n/a	n/a	n/a	derived	n/a
Duration of infusion	derived	sum	derived	sum	n/a
Duration of treatment	n/a	n/a	n/a	n/a	derived
Administered Volume (mL)	entered	sum	sum	sum	sum

Variable	Observation in database extract	Infusion	Day with Infusion	Week	Period
Total number of infusion sites	entered	max	n/a	n/a	n/a
Volume per Infusion Site (mL)	derived	derived	max	max	max
Infusion Rate per Infusion Site (mL/h)	derived	max	max	max	max
Number of Infusions	n/a	1	sum	sum	sum
Number of Days with Infusions	n/a	n/a	1	sum	sum

derived= see derivation rule below

sum= sum of values of the lower level of the same variable

max= maximum of the values of the lower level of the same variable

## Duration

Observation in database extract

duration (min) = end time (min) – start time (min)  
 if duration < 0 (ie, end is on the next day) then duration = duration + 24 × 60

## Days with infusion

The duration of infusions per day is the sum of the durations of the single infusions. In case of overlapping infusion times the duration of the infusions is the end of the last infusion that contributes to the overlap – the start of the first infusion that contributes to the overlap.

## Period

duration (days) =  
 last day of last week with IMP treatment in period – first day of first week in period + 1

Volume per Infusion Site (mL)

Observation in database extract

$$\text{volume per infusion site (mL)} = \frac{\text{administered volume (mL)}}{\text{total number of infusion sites}}$$

Infusion

$$\text{volume per infusion site (mL)} = \frac{\text{administered volume (mL)}}{\text{total number of infusion sites}}$$

Infusion Rate per Infusion Site (mL/h)

Observation in database extract

$$\text{infusion rate per infusion site (mL/h)} = \frac{60 \times \text{volume per infusion site (mL)}}{\text{duration (min)}}$$

Actual Total Dose (g)

Week

$$\text{actual total dose (g)} = 200 \text{ g/L} \times \text{administered volume (mL)} / 1000$$

if actual treatment = placebo, then actual total dose (g) = 0

Actual Dose (g/kg body weight)

Week

$$\text{actual dose (g/kg body weight)} = \text{actual total dose (g)} / \text{body weight (kg)}$$

body weight = last measurement before first dosing of the week

### 8.2.25 Prednisolone Equivalent Dose

Before the dose of oral concomitant corticosteroid treatment or oral rescue corticosteroid treatment is used in further derivations, it must be standardized using prednisolone equivalent doses. Each corticosteroid has its own factor (“Equivalent Dose”) as shown in [Table 7](#).

$$\text{dose (mg prednisolone equivalent)} = \text{dose (mg)} \times 20 / \text{Equivalent Dose}$$

---

**Table 7: Corticosteroid Dose Equivalency Table**

Corticosteroid (WHO DD Product Name)*	Equivalent Dose	Corticosteroid (WHO DD Product Name)*	Equivalent Dose
Prednisolone	20 mg	Betamethasone	2.4 mg
Prednisone	20 mg	Dexamethasone	3.0 mg
Methylprednisolone	16 mg	Hydrocortisone	80 mg
Triamcinolone	16 mg	Cortisone	100 mg
Meprednisone	16 mg		

\* all suffixes like acetate, sodium succinate, sodium phosphate, acetonide can be ignored for programming.

### 8.2.26 Change of Oral Concomitant Corticosteroid Treatment

The change of oral concomitant corticosteroid treatment compares the average daily doses of the treatment in the reference week and the week of interest. The dose at week 1 (ie, the baseline dose) is the dose administered at the baseline date.

$$\begin{aligned} \text{average daily dose week X (mg*)} = \\ \text{sum of all daily doses of week X (mg*) / length week X (days)} \end{aligned}$$

If the length of a week is 0 (see Section 8.2.3) the respective average daily dose will be set to the average daily dose of the subsequent week with length > 0.

#### Change in Week X, for X=2 to 197

$$\begin{aligned} \text{change (\%)} = \\ 100 \times [(\text{average daily dose week X (mg*)} - \text{baseline dose (mg*)}) / \\ \text{baseline dose (mg*)}] \end{aligned}$$

\* mg prednisolone equivalent

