average daily dose of Week 24 is reduced by at least 25%, as treatment with IgPro20 starts in both treatment sequences on the first day of Week 25.

For subjects who do withdraw from IMP or the study for reasons which are related to the Ukraine war before Week 25, the resulting missing values can be considered missing at random (MAR) and multiple imputation will be used to derive the hypothetical post-intervent event reduction of oral concomitant corticosteroid dose in percent (%reduction). Replacement of trailing missing %reduction values for weeks 17 to Week 24 (ie, monotone missings) will be done if the subject received oral corticosteroid medication at baseline using multiple imputations based on monotone regression with the covariates treatment, country, and Baseline MMT-8 ( $\leq$  142 points vs.  $>142$  points), baseline oral corticosteroid dose and %reduction values from previous weeks starting at Week 17 (50 imputations) by SAS® PROC MI. Note: If the subject did not receive any oral corticosteroid medication at baseline %reduction will be set to 0. The multiple imputation process will correspond to the one for the primary endpoint described in Section 10.2. A subject is considered a responder regarding this endpoint, if he/she is able to reduce the oral concomitant corticosteroid dose by at least 25% at Week 24, ie if %reduction is  $\geq 25$ .

For each of the 50 data sets resulting from the multiple imputation process the analysis of the 4th key secondary endpoint will be based on an exact logistic regression model including fixed effects for treatment, region (Japan vs. non-Japan), and Baseline MMT-8 ( $\leq$  142 points vs.  $>142$  points). The corresponding results across the data sets are combined for overall inference using SAS® PROC MIANALYZE according to Rubin's rule.

The 4 key secondary endpoints will be analyzed with an overall 1-sided alpha level of 0.025. The hypotheses associated with the key secondary endpoints will be formally tested and therefore adjusted for multiplicity. The key secondary analyses will be performed based on the mITT and repeated for the PP.

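### SAP 8.2.26 divides a weekly average steroid dose by a single-day baseline dose, so some unchanged alternate-day regimens count as a response on the fourth key secondary endpoint

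*SAP*

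**What the plan says.** SAP 8.2.26 opens with the principle that the change "compares the average daily doses of the treatment in the reference week and the week of interest". The next sentence sets the baseline side differently: "The dose at week 1 (ie, the baseline dose) is the dose administered at the baseline date". For Weeks 2 onward the average daily dose is the sum of the week's daily doses divided by the number of days in that week. The percent change is the weekly average minus the baseline dose, divided by the baseline dose.

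SAP 10.4 applies this to the fourth key secondary endpoint. Week 24 stands in for Week 25, and a responder is a subject "able to reduce the oral concomitant corticosteroid dose by at least 25% at Week 24". It adds: "Note: If the subject did not receive any oral corticosteroid medication at baseline %reduction will be set to 0". The endpoint is one of the four hypotheses tested under the Hommel procedure in SAP 4.2.2.

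Protocol 4.1.1 (inclusion criterion 6) and 7.2 ask for a stable dose of at most 20 mg/day prednisolone equivalent for one month before Baseline. Neither document requires equal doses on every day, excludes alternate-day dosing, or says how such a regimen becomes a baseline daily dose.

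**The concern.** The two opening sentences of 8.2.26 conflict, and the formula follows the second. Its numerator smooths variation within the week and its denominator does not. When daily doses differ, the result mixes any real change in dose with the accident of which day was the baseline date.

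This value decides response on a formally tested endpoint. It also feeds the 25%, 50% and 75% reduction endpoints in SAP Table 11, the exploratory percent reduction in Table 12 and the baseline dose covariate in the imputation model of 10.4. In 8.2.28, ADD_1 is by its footnote a Week 1 average, whereas 8.2.26 makes the Week 1 dose a single-day value, so the taper algorithm inherits the ambiguity.

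**Working it through.** **Plan's own figure.** The documents give no assumed rate, power or sample size for this endpoint. The only such figure is for the primary endpoint. SAP Table 3 implies responder probabilities of 0.65 × (0.9² + 0.1 × 0.2) + 0.35 × 0.2 × 0.9 = 0.6025 and 0.30 × (0.9² + 0.1 × 0.1) + 0.70 × 0.1 × 0.9 = 0.309. With 63 per arm, exact enumeration of the one-sided Fisher test at 0.025 gives power 0.904, against the stated 90%. That calculation does not use 8.2.26. Rescue treatment is identified from a CRF flag (8.2.27), so the primary endpoint does not depend on 8.2.26 either.

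**Formula (SAP 8.2.26, 10.4).** Change % = 100 × (Week 24 mean - D0) / D0, where D0 is the dose on the baseline date. Response means change ≤ -25%, that is, Week 24 mean ≤ 0.75 × D0.

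**Unchanged regimens, seven-day Week 24, baseline on the higher-dose day:**

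| Regimen (mg) | High days in Week 24 | Week 24 mean | Change | Responder |
|---|---|---|---|---|
| 20/0 alternating | 4 | (4×20)/7 = 11.43 | -42.9% | yes |
| 20/0 alternating | 3 | (3×20)/7 = 8.57 | -57.1% | yes |
| 10/5 alternating | 4 | (4×10+3×5)/7 = 7.86 | -21.4% | no |
| 10/5 alternating | 3 | (3×10+4×5)/7 = 7.14 | -28.6% | yes |
| 15/10 alternating | 4 or 3 | 12.86 or 12.14 | -14.3% or -19.0% | no |
| 10 every day | n/a | 10 | 0% | no |

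To count as a responder, the subject must also have had no rescue treatment and no withdrawal unrelated to the Ukraine war before Week 25.

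**Error in the other direction.** With 20/0 and an off day at baseline, D0 = 0 and the formula is undefined. With 10/5 and baseline on the 5 mg day, no change reads as +42.9% or +57.1%. A true 30% cut gives a mean of 7.14 × 0.7 = 5.0 or 7.86 × 0.7 = 5.5, which reads as 0% or +10%: a missed response.

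**Size, on assumed inputs only.** Suppose true response rates among baseline steroid users of 45% and 20% (odds ratio 3.27). Suppose a share f take 20/0-type regimens, half with a dosing day at baseline (all counted as responders) and half with an off day (all counted as non-responders). The observed rate is (1 - f) × p + f/2.

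| f | Observed rates | Odds ratio |
|---|---|---|
| 2% | 45.1% vs 20.6% | 3.17 |
| 5% | 45.25% vs 21.5% | 3.02 |
| 10% | 45.5% vs 23.0% | 2.79 |

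**Choice of averaging window.** A seven-day average at both ends is not enough. An unchanged 20/0 regimen with four dosing days in the baseline week and three in Week 24 gives (8.57 - 11.43)/11.43 = -25.0%, which meets the threshold. A 14-day baseline holds seven dosing days and averages 10 mg, so a seven-day Week 24 gives -14.3% or +14.3% and no response.

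**The case against.** The strongest reply is that the premise may never occur. The protocol writes oral steroid doses and taper steps in mg/day (5.3.2, 7.2), and for constant daily dosing the single-day value equals the average. Nothing in the documents shows that any subject takes an alternate-day regimen. SAP 8.2 also defers full derivation detail to separate dataset specifications, and the oral corticosteroid CRF is not among the documents. Either might already turn an alternate-day entry into a mean daily dose. This stands as a limit on the practical effect. It does not remove the contradiction in the SAP, and a rule that decides a confirmatory endpoint belongs there.

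Four stronger readings are tempting, and the documents do not support them:

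- **Any unequal-day regimen produces a false response.** It does not. 15/10 mg never does, and 10/5 mg does so only with three high days in Week 24.
- **An off-day subject becomes a non-user with the reduction set to 0.** That is one reading of 10.4. A subject with a continuing steroid record across Baseline is more naturally read as receiving it. The dilution figures above rest on counting these subjects as non-responders.
- **A missed tablet on the baseline date gives a zero baseline.** The only subject diary described is for infusions, and no daily tablet record is described.
- **The flaw favours IgPro20 or inflates type I error.** The misclassification comes from the dosing calendar, not from the arm.

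**Conclusion.** The concern holds in a bounded form. SAP 8.2.26 contradicts itself, and the rule it then applies gives a wrong value whenever daily doses differ. A false response arises when the Week 24 mean of an unchanged regimen is at most 75% of the baseline-date dose. Alternate-day dosing with a dosing day at baseline meets this in any seven-day week; 10/5 mg alternation meets it only in some weeks. With an off day at baseline the change is undefined.

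The number of affected subjects is unknown and may be zero. If there are some, the main harm is dilution of the treatment difference and misstated rates in both arms. The odds ratios above show how large this could be under assumed inputs and are not estimates for this trial. The point merits correction because the endpoint is formally tested and the repair is simple.

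**What to change.** Before unblinding, reconcile the two sentences in SAP 8.2.26 by defining the baseline dose as the average daily prednisolone-equivalent dose over the 14 days before first IMP. Use that one value in the change formula, as ADD_1 in 8.2.28, as the baseline dose covariate in the imputation model, and to identify baseline steroid users in 10.4.

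One limit should be checked in the data. Study weeks run from infusion to infusion (8.2.3), so Week 24 need not be seven days. For strict alternate-day dosing and a Week 24 of L days, L odd, the largest spurious fall against the 14-day baseline is 100/L percent: 14.3% for seven days, 20% for five, 33.3% for three. Only a Week 24 of three days or fewer could still cross the threshold.

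The cost is a wording change and one derivation. No new data are needed: Protocol 8.4 already has medications from the three months before Baseline recorded in the eCRF, and the 14 days fall inside the required month of stable dosing. Values for constant daily dosing do not change.

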  - HbA1c
  - Muscle enzymes
  - Other biochemistry
  - Coagulation
  - Serum IgG
  - ANA, MSA, and MAA
- Subject SC Infusion Diary review
- Document AEs
- Document concomitant therapies
- Document any change to physiotherapy since the previous study visit
- DOW assessment
- Assess if subject has clinically relevant improvement, and if so, subjects must initiate oral corticosteroid taper (see [Section 5.3.2](#))
- Individual CSMs

- CDASI
- 5-D Itch Score
- Timed Up and Go
- EQ-5D-5L, WPAI-GH, TSQM-9

### 8.5.4 Study Period 2

During Study Period 2, all participating subjects will receive 28 weeks of active treatment with IgPro20 at 0.5 g/kg SC on a weekly basis. Study Period 2 starts with administration of IgPro20 at Week 25, after all Week 25 assessments (as specified in [Section 8.5.3.8](#)) have been completed. Study Period 2 continues through the Week 53 Visit when the subject's eligibility for continuation of IgPro20 treatment in Study Period 3 will be confirmed ([Section 8.5.4.7](#)). Subjects not eligible for participation in Study Period 3 must complete the Week 56 Safety Follow-up Telephone Call ([Section 8.5.4.8](#)).

Study assessments will be performed as specified in the Schedule of Assessments for Study Period 2 ([Table 2](#)).

#### 8.5.4.1 Week 29

The following procedures will be conducted at 28 weeks  $\pm$  3 days after the first SC infusion of IMP:

- Body weight
- IMP assignment
- Vital signs
- Safety assessments
- Collection of urine sample for hCG pregnancy test, if applicable
- Collection of blood samples to assess the following:
  - Muscle enzymes
  - Coagulation
- Subject SC Infusion Diary review
- Document AEs
- Document concomitant therapies

- Document any change to physiotherapy since the previous study visit
- Assess if subject has clinically relevant improvement, and if so, initiate oral corticosteroid taper
- Individual CSMs
- CDASI

#### 8.5.4.2 Week 33

The following procedures will be conducted at 32 weeks  $\pm$  3 days after the first SC infusion of IMP:

- Body weight
- IMP assignment
- Vital signs
- Safety assessments
- Collection of urine sample for hCG pregnancy test, if applicable
- Collection of blood samples to assess the following:
  - Hematology
  - Muscle enzymes
  - Other biochemistry
  - Coagulation
- Subject SC Infusion Diary review
- Document AEs
- Document concomitant therapies
- Document any change to physiotherapy since the previous study visit

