The analysis of the fourth key secondary endpoint, ie, the proportion of subjects who are able to reduce the oral concomitant corticosteroid dose by at least 25% at Week 25 will be done in analogy to the analysis of the primary endpoint (see [Section 10.3](#)).

For subjects who do withdraw from IMP or the study for reasons which are related to the Ukraine war before Week 25, the resulting missing values can be considered missing at random and multiple imputation will be used to derive the hypothetical post-intercurrent event reduction of oral concomitant corticosteroid dose in percent (%reduction).

Replacement of trailing missing %reduction values for Week 17 to Week 25 (ie, monotone missings) will be done if the subject received oral corticosteroid medication at baseline using multiple imputations based on monotone regression with the covariates treatment, country, and Baseline MMT-8 ( $\leq 142$  points vs.  $> 142$  points), baseline oral corticosteroid dose and %reduction values from previous weeks starting at Week 17 (50 imputations) by SAS® PROC MI. Note: If the subject did not receive any oral corticosteroid medication at baseline %reduction will be set to 0. The multiple imputation process will correspond to the one for the primary endpoint described in [Section 10.4.2.3](#). A subject is considered a responder regarding this endpoint, if he/she is able to reduce the oral concomitant corticosteroid dose by at least 25% at Week 25, ie if %reduction is  $\geq 25$ .

For each of the 50 data sets resulting from the multiple imputation process the analysis of the 4th key secondary endpoint will be based on an exact logistic regression model including fixed effects for treatment, region (Japan vs. non-Japan), and Baseline MMT-8 assessment ( $\leq 142$  points vs.  $> 142$  points). The corresponding results across the data sets are combined for overall inference using SAS® PROC MIANALYZE according to Rubin's rule.

The 4 key secondary endpoints will be analyzed with an overall 1-sided alpha level of 0.025. The hypotheses associated with the key secondary endpoints will be formally tested and,

---

therefore, adjusted for multiplicity as described in Section 10.4.2.4.4. The key secondary analyses will be performed based on the mITT and repeated for the PP.

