### **8.2.3 Study Week**

The start of a study week is the day of the first infusion of IMP in that week as recorded in the eCRF. For efficacy, the assessments within 7 days following the IMP discontinuation will be included in the analysis if no rescue medication was administered before the respective assessment.

The end of a study week is the day before the start of the next week. In case of missing exposure weeks as recorded in the eCRF planned weeks will be considered as described below.

- End date of the last non-missing week prior to a missing week is 6 days after its start or one day before the start of the next non-missing week (whatever is first).
- End date of the last missing week is 1 day before the start of the next non-missing week.
- In case of multiple consecutively missing weeks, the total gap time is equally distributed across all missing weeks.

In case there is no gap to include a planned missing week between 2 consecutive non-missing weeks the respective week will be flagged in the listings and the length of the planned week will be 0 (see below).

The end of the last week will be defined as follows:

---

end date of last week = minimum of  
(date of EOP, maximum of (date of 1st infusion in last week + 6 days, date of last administration  
of last week))

For the calculation of average daily dose of oral concomitant corticosteroid treatment, the length  
of a week will be calculated as

$$\text{length of week X (days)} = \text{maximum of (0, end date of week X} - \text{start date of week X} + 1)$$

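### A zero-length Week 24 is filled with a Study Period 2 corticosteroid dose, contrary to the SAP's own reason for scoring the fourth key secondary endpoint at Week 24

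*SAP*

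**What the plan says.** Three SAP rules meet here.

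- **Scoring week.** SAP 10.4 treats the Week 25 dose as reduced when the "average daily dose of Week 24 is reduced by at least 25" per cent. Its reason is "as treatment with IgPro20 starts in both treatment sequences on the first day of Week 25".
- **Week length.** SAP 8.2.3 places missing exposure weeks between the recorded ones. If there is no gap for a missing week, "the respective week will be flagged in the listings and the length of the planned week will be 0".
- **Fill.** For a week of length 0, SAP 8.2.26 states that "the respective average daily dose will be set to the average daily dose of the subsequent week with length > 0".

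SAP 8.2.24 assigns Weeks 25 to 52 to Study Period 2. SAP 10.4 does limit data to the end of Period 1, but only for the MMRM analyses, which do not include this endpoint.

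At the Week 25 visit, Protocol 8.5.3.8 instructs: "Assess if subject has clinically relevant improvement, and if so, subjects must initiate oral corticosteroid taper". Protocol 8.5.4 starts Study Period 2 with the first Week 25 infusion, after the Week 25 assessments are complete.

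The protocol itself names Week 25. Section 10.4.2.4.3 refers to "Replacement of trailing missing %reduction values for Week 17 to Week 25" and defines response at Week 25. SAP 5 reports no changes from the protocol's planned analyses.

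**The concern.** SAP 10.4 chooses Week 24 in order to keep Study Period 2 doses out of a Study Period 1 endpoint. The fill rule lets them back in for any subject whose Week 24 has length 0, and nothing stops the fill at the period boundary. The imported dose can also differ for a structural reason: a taper step decided at the Week 25 visit is in force before the first Week 25 infusion, so it shows in the Week 25 dose but not in the Week 24 dose.

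The endpoint is one of four tested under the Hommel procedure at an overall 1-sided 0.025. The outcome is binary and the counts are modest, so a rule that misclassifies even a few subjects should be corrected before unblinding.

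**Working it through.** No sample size, power or alpha in the plan depends on this rule, so there is no stated figure to reproduce. The check applies the SAP's rules and the protocol's taper schedule to dated examples.

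**1. When Week 24 has length 0.** Let S be the first infusion day of Week 23 and T that of Week 25, with Week 24 missing. By SAP 8.2.3, Week 23 ends at the earlier of S + 6 and T − 1, and Week 24 runs from the next day to T − 1. So

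length of Week 24 = max(0, T − S − 7).

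It is 0 whenever T − S ≤ 7. With S = 163 and T = 170 it is 0; with T = 171 it is 1. When it is 0, T − 1 ≤ S + 6, so Week 23 runs up to the day before the Week 25 infusion.

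**2. Assumed dates.** Day 1 is the first infusion. The Week 21 visit is day 141 and the Week 25 visit day 169. S = 163 and T = 170. Week 23 is then days 163–169 and Week 25 days 170–176.

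**3. Taper (Protocol 5.3.2, followed exactly).** From 10 mg or less: 1 mg/day every 2 weeks. From 11 to 20 mg: 2.5 mg/day every 2 weeks down to 10 mg (taken here as stopping at 10), then 1 mg/day every 2 weeks. Taper from Week 21 has steps on days 141, 155 and 169.

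**4. Score.** % reduction = 100 × (baseline − average daily dose) / baseline; responder if ≥ 25.

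For 10 mg with taper from Week 21, the dose is 8 mg from day 155 and 7 mg from day 169:

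- seven days before the visit: 8.0 mg, 100 × 2/10 = 20.0%, non-responder
- Week 23: (6 × 8 + 7)/7 = 7.86 mg, 21.4%, non-responder
- Week 25, the SAP fill: 7.0 mg, 30.0%, responder

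Other results in mg (% reduction):

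| Baseline | Taper from | 7 days before visit | Week 23 | Week 25 (SAP fill) |
|---|---|---|---|---|
| 9 | Week 21 | 7.00 (22.2) | 6.86 (23.8) | 6.00 (33.3) |
| 9.5 | Week 21 | 7.50 (21.1) | 7.36 (22.6) | 6.50 (31.6) |
| 11 | Week 21 | 9.00 (18.2) | 8.86 (19.5) | 8.00 (27.3) |
| 11.5 | Week 21 | 9.00 (21.7) | 8.86 (23.0) | 8.00 (30.4) |
| 13 | Week 21 | 10.00 (23.1) | 9.86 (24.2) | 9.00 (30.8) |
| 4 | Week 25 | 4.00 (0.0) | 3.86 (3.6) | 3.00 (25.0) |

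Baseline doses from 1 to 20 mg were run in 0.5 mg steps:

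- **Taper from Week 21:** the classification changes at 9, 9.5, 10, 11, 11.5 and 13 mg. At 8.5 mg Week 23 already gives 25.2%, so the two fills agree.
- **Taper first started at Week 25:** it changes at every dose from 1 to 4 mg, because one 1 mg step is at least 25% of 4 mg or less.
- **Taper from Week 17:** no change, because 25% is reached before Week 24.

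**5. The other direction.** Protocol 5.3.2 allows the dose to be raised, up to 125% of Baseline, if symptoms increase during taper. Take a 10 mg subject at 7 mg through Week 23 (30%) who is raised to 8 mg from Week 25 (20%). The fill turns a responder into a non-responder.

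**6. Size per subject.** With 63 subjects per arm as planned, one reclassified subject moves that arm's rate by 1/63 = 1.6 percentage points.

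**The case against.** The strongest reply is that this is rare and nearly harmless. A reclassification needs all of the following: a missed Week 24 with Week 25 within 7 days of the start of Week 23, although Protocol 5.1.3 expects each week's infusions before the next visit; oral corticosteroid at baseline, since otherwise the reduction is set to 0; and a taper start and baseline dose in the ranges above. Taper is also as tolerated, so few subjects will follow the schedule exactly. This stands, and it limits the point to a small one. The version 5 entry in the SAP's modification history lists a rule for weeks of length 0, so such weeks were foreseen, but no count is given.

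A second reply is that the protocol's endpoint is at Week 25, so the fill lands close to it. That is no defence of the SAP, which moved scoring to Week 24 deliberately and gave its reason. Flagging such weeks in listings makes them visible but leaves the derived value unchanged. The separate dataset specifications mentioned in SAP 8.2 may say more, but they are not available here.

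A reader might infer three stronger things that the documents do not support.

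- **That errors always favour responder status.** They do so only for a subject who keeps tapering; a permitted increase reverses the error.
- **That the switch to IgPro20 drives the effect.** Sequence A has no switch. In every example with continued taper the change comes from the Week 25 taper step, decided on assessments made before the first Study Period 2 infusion, and it can occur in either arm. If a first IgPro20 week did lower doses in Sequence B, it would raise the placebo rate and dilute the contrast.
- **That type I error is inflated.** The rule is the same in both arms, and subjects and site staff stay blinded through Study Period 2. Nothing shows a systematic advantage for IgPro20.

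**Conclusion.** The inconsistency is real and lies within the SAP: 10.4 keeps Study Period 2 doses out of this endpoint, while 8.2.3 and 8.2.26 together admit them when Week 24 has length 0. Misclassification is possible in either arm and in either direction. Upward errors arise with taper from Week 21 at baseline doses of about 9–10, 11–11.5 and 13 mg, and with taper first started at Week 25 at 4 mg or less. These ranges assume the dates shown and exact adherence to the taper schedule.

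The effect on the test cannot be sized, because the documents give no frequency for a zero-length Week 24. It is probably small: 1.6 points in one arm's rate for each reclassified subject, and few subjects are likely to meet every condition. The point is worth making because a formally tested endpoint should not rest on a fallback that contradicts its own definition. That SAP 5 does not record the move from the protocol's Week 25 to Week 24 is a documentation matter only, since SAP 10.4 states the move and its reason openly.

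**What to change.** Add one sentence to SAP 8.2.26: for the Study Period 1 corticosteroid reduction endpoint, a zero-length Week 24 takes the average daily dose of the last preceding Study Period 1 week with length above 0, and no value is filled across the Week 24/25 boundary. If that week is Week 23, it already covers the days up to the Week 25 infusion, so the filled value is not out of date.

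Leave the rule for other weeks as it is. A general carry-forward would disturb taper detection in SAP 8.2.28, which requires the dose in Week X+1 to be strictly below that in Week X: a zero-length Week X+1 given Week X's dose could never meet that condition.

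For documentation, note in SAP 5 that the protocol's Week 25 is operationalised as Week 24 for this endpoint.

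The cost is one sentence in each section and one conditional in the derivation program, before unblinding. No additional data are needed.
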